5.2.12 Patient and Informant Satisfaction Question

Data will be collected by the Handheld Device and the analysis method will not be covered by this SAP.

5.3 Analysis Visit Windows

Baseline of the study is defined as the last non-missing result, including results from repeated and unscheduled measurements, prior to first dosing.

Efficacy and safety assessments will be summarized by analysis visit as presented in Table 1 below.

Table 1 Analysis Visit Windows

Analysis Visit	Study Visit	Target Study Day @	Study Day Interval
Baseline (Day 1)	2 (Week 0)	1	≤ 1
Week 1	3 (Week 1)	8	2 – 11
Week 2	4 (Week 2)	15	12 – 18
Week 3	5 (Week 3)	22	19 – 25
Week 4	6 (Week 4)	29	26 – 32
Safety Follow-up	7 (Week 8)	59	≥ 33

@ Derivation of study day: study day = assessment date - first dose date + 1 if the assessment date \geq first dose date, otherwise study day = assessment date – first dose date. Study day 1 is the day of first administration of study drug (pimavanserin, quetiapine, or placebo).

5.3.1 Unscheduled Assessments

Both Scheduled and Unscheduled assessments, including the assessments at early termination visits, will be used for planned timepoint analyses. All assessments will be presented in data listings.

5.3.2 Multiple Measurements within Visit Windows

In the event that more than one assessment falls within a given window the assessment closest to the target study day will be selected for the by-visit analysis. If two assessments are equidistant from the target study day then the chronologically last assessment will be used. Exceptions may be made for incomplete assessments, in which case, more complete assessments may be given priority. Details are provided in a separate programming conventions document.

For safety analyses where the extreme values should be selected (e.g., overall post-Baseline minimum, overall post-Baseline maximum, and potentially clinically important values), all non-missing post-Baseline values should be considered, regardless of whether the value is selected for the by-visit summaries. All assessments will be presented in data listings.

5.4 Missing or Incomplete Date for Last Dose of Study Drug

In the Safety Analysis Set, if the last dose date of study drug is missing for a subject who completed or early terminated from the study, then it will be imputed using the last expected dosing date (LED), defined as the earlier of the following three dates: the date of the end-of-treatment (EOT)/early termination (ET) visit, the last expected dosing date per protocol, and the kit return date of the last dispensed drug kit. For the incomplete last dose date of study drug, the imputation algorithms will be detailed in the analysis dataset specification document. The missing or incomplete dates will be displayed in the data listings as reported on the eCRF rather than the imputed dates.

5.5 Missing or Incomplete Dates for Prior or Concomitant Medications

Missing or incomplete medication start or stop dates will be imputed for the purpose of determining whether the medication is taken concomitantly or not (see Section 11 for definition). When the chronological order of medication use relative to the study drug treatment period is unclear due to missing or incomplete date(s), the medication will be considered as concomitant. The imputation algorithms will be detailed in the analysis dataset specification document. The missing or incomplete dates as captured on the eCRF will be displayed in the data listings.

5.6 Missing or Incomplete Date for Adverse Events

Missing or incomplete adverse event (AE) start dates will be imputed for the purpose of determining whether the AEs are treatment-emergent or not (see Section 14.1 for definition). When the chronological order of an AE onset relative to the study drug treatment period is unclear due to missing or incomplete date(s), the AE will be considered as treatment-emergent. The imputation algorithms will be detailed in the analysis dataset specification document. The missing or incomplete dates captured on the eCRF will be displayed in the data listings.

5.7 Missing Severity Assessment for Adverse Events

If the severity is missing for an AE starting on or after the date of the first dose of study drug, then a severity of “Severe” will be assigned. The imputed values for severity assessment will be used for incidence summaries, while the actual values will be used in data listings.

5.8 Missing Relationship to Study Drug for Adverse Events

If the relationship to study drug is missing for an AE starting on or after the date of the first dose of study drug, a causality of “Related” will be assigned. The imputed values for relationship to study drug will be used for incidence summaries, while the actual values will be presented in data listings.

5.9 Character Values of Clinical Laboratory Variables

If the reported value of a clinical laboratory variable cannot be used in a statistical analysis due to, for example, a character string reported for a numeric variable, an appropriately determined coded value may be used in the statistical analysis. The coding algorithms will be detailed in the analysis dataset specification document. The actual values as reported in the database will be presented in data listings.

6. SUBJECT DISPOSITION

For subjects who participate in the screening phase but are not randomized (screen failures), their demographics information (including age, sex, and primary race), screen failure reasons (the specific inclusion/exclusion criterion, or criteria, not met or other reasons including the reason due to COVID-19) and protocol version will be listed. If a subject is re-screened, then the re-screening subject ID and the final enrollment status (whether eventually enrolled) will also be displayed in this listing. In addition, the frequency that the screen failure reasons are reported will also be summarized. Note that one subject may be deemed ineligible for multiple inclusion/exclusion criteria and may be allowed to rescreen with the permission of the Medical Monitor, provided the screen failure was due to a temporary condition that subsequently resolved.

The number of sites that screened at least 1 subject, number of sites that randomized at least 1 subject, number of subjects screened, and number of unique subjects screened will be tabulated. In addition, the number of subjects enrolled at each site will also be tabulated by analysis set and by treatment group and overall.

For randomized subjects, the number and percentage of subjects in the Safety Analysis Set and Exploratory Analysis Set will be summarized by treatment group and overall. A listing will be provided displaying all subjects excluded from the Safety or Exploratory Analysis Sets, and will include reason(s) for exclusion.

Within each analysis set, the number and percentage of subjects who completed the study or discontinued (all discontinued and by discontinuation reasons including the reason due to COVID-19) will also be summarized by treatment group and overall.

7. PROTOCOL DEVIATIONS

Protocol deviations will be reviewed periodically over the course of the study. The review process, definition of the deviation categories, and the classification of a deviation as major or minor are detailed in the Protocol Deviation Management Plan. Protocol deviations will also be assessed with respect to relationship to COVID-19.

A summary of the number and percentage of subjects with major protocol deviations for each deviation category will be presented by treatment group for the Randomized Analysis Set in three ways: all protocol deviations, COVID-19 related protocol deviations, and non COVID-19 related protocol deviations.

Two listings of major protocol deviations will be provided: all deviations and non COVID-19 related protocol deviations. A listing of all COVID-19 related protocol deviations including the major and the minor will be provided.

8. DEMOGRAPHICS AND OTHER BASELINE CHARACTERISTICS

Demographics and baseline characteristics will be summarized by treatment group and overall for the Randomized and Safety analysis sets, using descriptive statistics. Variables include age, sex, race, ethnicity, height, weight, and BMI.

Race will also be categorized by White vs. Non-White. The reported age reflects a subject's age at the informed consent date.

Parkinson's disease history will be summarized by treatment and overall for the Randomized and Safety analysis sets using descriptive statistics. Variables include Age at Parkinson's disease diagnosis, prior antipsychotic use (yes/no), and presence of insomnia (yes/no).

9. MEDICAL HISTORY

Medical history reported terms will be coded with Medical Dictionary for Regulatory Activities (MedDRA), version 23.0 or newer. The subject incidence will be summarized for each system organ class (SOC) and preferred term by treatment group and overall for the Safety Analysis Set. A subject will be counted only once per SOC or per preferred term for the summary.

A listing of the SOC, preferred term, body system, verbatim for the medical history condition/event, start and stop dates (when available), and an indicator for whether or not the condition is ongoing will be provided.

10. EXTENT OF EXPOSURE AND TREATMENT COMPLIANCE

Extent of exposure and treatment compliance will be summarized as continuous variables by treatment group for the Safety Analysis Set.

10.1 Exposure to Study drug

Duration of exposure to study drug will be calculated for each subject as (last dose date – first dose date + 1). The number and percentage of subjects within each of the following exposure levels in terms of duration of exposure will also be tabulated: <1 week (1 to 6 days), 1 to <2 weeks (7 to 13 days), 2 to <3 weeks (14 to 20 days), 3 to <4 weeks (21 to 27 days), and >4 weeks (28 days or longer).

10.2 Measurement of Treatment Compliance

Study drug dosing compliance is defined as the total number of tablets actually taken by a subject divided by the number of tablets expected to be taken and then multiplied by 100. The total number of tablets actually taken is calculated by the total number of tablets dispensed minus the number of tablets returned. The number of tablets expected to be taken is calculated as the duration of exposure multiplied by 2 (the planned number of tablets taken per day).

Treatment compliance will also be summarized as a categorical variable. The number and percentage of subjects within each of the following compliance levels will be tabulated: <80%, 80 to 120%, and >120%.

11. PRIOR, CONCOMITANT, AND POST-TREATMENT MEDICATION

Prior medication is defined as any medication with the start and stop dates prior to the date of the first dose of study drug. Concomitant medication is defined as any medication with a start date prior to the date of the first dose of study drug and continuing past the first dose of study drug or with a start date between the dates of the first and last doses of study drug, inclusive. Any medication with a start date after the date of the last dose of study drug will be considered as post-treatment medication. Medications will be coded using WHO Drug Dictionary March 2018 or newer version. The number and percentage of subjects taking each drug class (ATC Level 3) and medication preferred term will be tabulated by treatment group and overall for the Safety Analysis Set. Multiple medication usage by a subject in the same category will be counted only once.

Prior and Concomitant Medications

Prior and concomitant medications will be summarized for the Safety Analysis Set by ATC Level 3, preferred term, and the study drug (placebo, quetiapine, and pimavanserin).

Post-Treatment Medications

Post-treatment medications will be summarized for the Safety Analysis Set by ATC Level 3, preferred term, and the study drug (placebo, quetiapine, and pimavanserin) of which subjects received their last doses.

COVID-19 Related Medications

Relationship to COVID-19 will be assessed for selected medications as detailed in the GSD. COVID-19 related concomitant medications will be listed separately.

12. EFFICACY ANALYSES

All efficacy analyses will be performed using the planned treatment assignments based on the randomization schedule for the Exploratory Analysis Set.

12.1 Efficacy Variables

Exploratory Efficacy Endpoints Measured at Study Visits

- Change from Baseline to Week 4 in
 - Time to completion or maximum time of TMT Parts A and B,
 - HVLT-R recognition discrimination index, and
 - PD NMS total score
- CGI-I score at Week 4
- PGI-I score at Week 4

12.2 Adjustment for Covariates

The corresponding baseline value will be included as a covariate for the analysis of time to completion or maximum time of TMT Parts A and B, HVLT-R recognition discrimination index, and PD NMS total score. Baseline CGI-S score will be used as a covariate for the CGI-I analysis.

12.3 Handling of Missing Data

Missing data will not be imputed in the analysis of exploratory efficacy endpoints.

12.4 Multiple Comparisons / Multiplicity

Multiplicity will not be adjusted in the analysis of exploratory efficacy endpoints due to the exploratory nature of this trial.

12.5 Examination of Subgroups

No subgroup analyses are planned.

13. METHODS OF EFFICACY ANALYSES

The change from Baseline in the exploratory efficacy endpoints measured at scheduled visits including time to completion or maximum time of TMT Parts A and B, HVLT-R recognition discrimination index, and PD NMS total score will be analyzed using an analysis of covariance model (ANCOVA) using observed scores. The model will include treatment group as a factor and the corresponding Baseline measure as a covariate.

Summary statistics (observed and change from Baseline), LS means, the between-group differences (Pimavanserin – Placebo and Quetiapine – Placebo) in LS means with the corresponding 95% confidence intervals, p-values, and the effect sizes (Cohen's d) will be presented at each post-Baseline visit for the Exploratory Analysis Set.

CGI-I score will be analyzed using a similar ANCOVA model with treatment group as a factor and Baseline CGI-S score as a covariate.

PGI-I score will be analyzed using an analysis of variance model with treatment group as a factor.

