1.4 Study Rationale

This is a pilot, hypothesis-generating study to explore the effects of pimavanserin and low-dose quetiapine in subjects with PD that will be used to guide the design of future studies. In addition, the present study will explore the sensitivity of assessments/instruments (Ecological Momentary Assessments [EMAs] on the handheld device and actigraphy) that are novel for evaluating the experience of subjects with PD with respect to sedation/sleep, cognition, and other non-motor symptoms.

Pimavanserin is the only medication approved in the US for the treatment of hallucinations and delusions associated with PDP. The safety database supporting the approval of pimavanserin consisted of >1200 patients and healthy subjects, including >600 PDP patients, representing the largest development program in PDP ever conducted. In the PDP development program, pimavanserin demonstrated statistically significant improvement on measures of hallucinations and delusions, caregiver burden, clinical global impression, nighttime sleep and daytime sleepiness. Antipsychotic benefits have also been shown in subjects with Alzheimer's disease psychosis (ADP). Pimavanserin is currently being investigated in other neuropsychiatric conditions, including schizophrenia, major depressive disorder (MDD), and neurobehavioral symptoms of neurodegenerative disorders.

Low-dose quetiapine (50-100 mg daily) is commonly used off-label to treat neurobehavioral disturbances in the PD population, despite limited efficacy data supporting its use and clinically meaningful safety concerns ([Chen 2018](#)). Even at low doses, daytime sedation has

been reported with quetiapine, and is associated with worsened cognition, dizziness, decreased daytime activities and increased risk of falls in this vulnerable population.

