3.3 Randomization

Eligible subjects will be randomized into one of three treatment groups (pimavanserin, quetiapine, or matching placebo) in a 1:1:1 ratio using an Interactive Response Technology (IRT) system. The assignments will be based on a pre-generated permuted-block randomization schedule.

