3.5 Determination of Sample Size

This is a pilot study and is not powered for statistical significance. Up to 60 subjects will be randomized into the study.

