19. CHANGES TO ANALYSES SPECIFIED IN PROTOCOL

Because this trial was stopped early after randomizing only 11 subjects, all of the mixed-model repeated measures analyses were changed to ANCOVA in order to minimize possible non-convergence issues.

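### SAP 13 reports Cohen's d on at most 11 subjects with no stated small-sample correction, standardising SD or confidence interval; in expectation d is inflated away from zero by about 11–13%, and by more if data are missing.

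*SAP*

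**What the plan says.** For the two active-minus-placebo contrasts, SAP 13 lists LS means, their differences with 95% confidence intervals, p-values, and Cohen's d as the effect size; all of these "will be presented at each post-Baseline visit for the Exploratory Analysis Set". The intervals named there belong to the LS-mean differences. No formula, standardiser, correction or interval is given for d.

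The models are also in SAP 13. For TMT, HVLT-R and PD NMS, "The model will include treatment group as a factor and the corresponding Baseline measure as a covariate"; CGI-I is handled in the same way with Baseline CGI-S. For PGI-I, "PGI-I score will be analyzed using an analysis of variance model with treatment group as a factor".

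The planned size in SAP 3.5 was "Up to 60 subjects will be randomized into the study". SAP 19 explains the move from MMRM to ANCOVA: "Because this trial was stopped early after randomizing only 11 subjects". It does not mention the effect size. SAP 3.6 dates the permanent stop to 24 September 2020, and SAP 20.1 dates version 1.0 to 19 October 2020. Protocol 1.4 says that the study "will be used to guide the design of future studies".

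**The concern.** Cohen's d divides a mean difference by an estimated SD. With few degrees of freedom the reciprocal of that SD is too large on average, so d is too large in absolute value on average. The effect is negligible at 60 subjects but not at 11. The SAP changed its model because of the small N, yet specified an effect size that is sensitive to the same problem.

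The bias acts in the same proportion on every endpoint, contrast and visit that has the same df, so reading across the table does not average it out. Because the standardiser is not named, a reader cannot tell which df apply or reproduce d. Because no interval for d is planned, nothing beside d shows how imprecise it is. In a study meant to inform later designs, a standardised effect is a natural number to pick up.

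**Working it through.** The documents give no effect-size, power or bias figure, so there is nothing of theirs to reproduce.

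**Inputs**
- 11 randomized (SAP 19); up to 60 planned (SAP 3.5).
- Three arms, 1:1:1: "The assignments will be based on a pre-generated permuted-block randomization schedule" (SAP 3.3). Arm counts and block size are not stated; about 4/4/3 is an assumption.
- ANCOVA fits 3 group means and 1 slope, so residual df = 11 − 4 = 7. The PGI-I ANOVA has 11 − 3 = 8.
- These are maxima. Replaced subjects leave the Exploratory Analysis Set (SAP 4) and missing data are not imputed (SAP 12.3). Two missing subjects bring the ANCOVA to 5 df, three to 4 df.
- A two-arm pooled SD has 6 df (4+4), 5 df (4+3) or 4 df (3+3).

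**Formula.** E[d] = δ / J(df), with J(df) = Γ(df/2) / [√(df/2) · Γ((df−1)/2)]. For example, J(7) = 3.3234 / (1.8708 × 2) = 0.888, and 1/0.888 = 1.126.

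| df | Case | J | Expected inflation, 1/J − 1 |
|---|---|---|---|
| 56 | ANCOVA, 60 subjects | 0.987 | 1.4% |
| 8 | ANOVA, 11 subjects (PGI-I) | 0.903 | 10.8% |
| 7 | ANCOVA, 11 subjects | 0.888 | 12.6% |
| 6 | 4+4 pooled SD, or ANCOVA with 1 missing | 0.869 | 15.1% |
| 5 | 4+3 pooled SD, or ANCOVA with 2 missing | 0.841 | 18.9% |
| 4 | 3+3 pooled SD, or ANCOVA with 3 missing | 0.798 | 25.3% |

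**Bias against sampling error.** Simulation with 200,000 replicates, three-arm ANCOVA, a 4 v 4 contrast and an assumed true d of 0.5:
- mean 0.561, median 0.518, SD 0.924;
- central 95% range −1.15 to 2.53;
- d above its true value in 50.9% of replicates, and of the wrong sign in 25.4%.

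For a 4 v 3 contrast the SD is 0.995. With a true effect of zero the mean is zero to within simulation error.

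**What the correction gains in the 4 v 4 case.** Multiplying by 0.888 gives mean 0.888 × 0.561 = 0.498 and SD 0.888 × 0.924 = 0.821. Mean squared error falls from 0.924² + 0.061² = 0.857 to about 0.821² = 0.674, a reduction of about 21%.

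**If d were used for sizing.** N scales as 1/d², so a d exactly equal to its inflated expectation would give J² of the required N: 0.789 at 7 df and 0.637 at 4 df. With an assumed true d of 0.5, two-sided 5% and 80% power (normal approximation), 63 per arm are needed. The inflated d would give 50 (7 df) to 40 (4 df), with true power of 70.5% to 60.9%. This is a conditional illustration, not an expected outcome.

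**The case against.** The strongest reply is that imprecision, not bias, is the problem. At a true d of 0.5 the bias of about 0.06 is under 1% of the mean squared error, the median of d is only about 4% high in the ANCOVA case, and one estimate in four has the wrong sign. That is correct, and it limits how much the point matters. It does not argue for leaving d as it is, since g is unbiased and also has the smaller variance. The trade is that the median of g is 0.888 × 0.518 = 0.46, a little below the true 0.5.

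A second reply is that g can be recovered by any reader from d and the df. That works only once the standardiser is known, and SAP 13 does not give it. SAP 1 places table specifications in a separate document, so the absence of a correction is inferred from the label and the missing formula. The choice of estimator is still a method, and belongs in SAP 13.

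Three stronger readings are tempting, and the documents do not support them:
- A reader might infer that the next trial will be undersized by 21–36%. No section says that d will set a sample size; Protocol 9.2 disclaims definitive comparisons; and the shortfall needs d to equal its inflated mean.
- A reader might infer that d is biased upward. The bias is away from zero. For TMT time, PD NMS, CGI-I and PGI-I a higher score is worse, so a benefit is a negative difference and is pushed further below zero.
- A reader might infer that d was carried over from the 60-subject plan. Protocol 9.5.2.1 plans no effect size; d appears in a SAP dated after the stop.

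**Conclusion.** The point holds as one of estimation and reporting. SAP 13 specifies Cohen's d for at most 11 subjects without a stated correction, standardiser or interval. The expected inflation is 10.8% (PGI-I) to 12.6% (ANCOVA endpoints), given all 11 subjects analysed and the model residual SD. It reaches 18.9–25.3% at 5 to 4 df, and is zero when the true effect is zero. The higher figures need missing or excluded subjects or a two-arm SD, none of which the documents establish.

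If d were used to size a later trial it would tend to mislead, but mainly because its SD is about 0.9. The primary TEAE analysis is unaffected, and so are the handheld-device and actigraphy analyses, which SAP 1 assigns to a separate plan.

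**What to change.** In SAP 13:
1. Name the SD that standardises the effect size, for example the model residual SD, and its df.
2. Replace Cohen's d with Hedges' g, that is d × J at the df of that SD, with a 95% CI at each visit. At 8 and 7 df J is 0.903 and 0.888; it should be recomputed where missing data lower the df.
3. State that an effect size from 11 subjects should not by itself set the sample size of a later trial.

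The cost is a few lines in the SAP, one multiplier and an interval in the program, and slightly smaller reported effect sizes. No new data are needed.
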